### PROTOCOL AMENDMENT SUMMARY OF CHANGES

DOCUMENT HISTORY		
Document	Date	
Amendment 2	23 September 2020	
Amendment 1	07 April 2020	
Original Protocol	06 September 2019	

### Amendment 2 (23 September 2020)

The changes and rationale for the changes from the Protocol Amendment 1 dated 07 April 2019 to Amendment 2 dated 23 September 2020 are as follows. Wording that has been deleted will be indicated with a strikethrough (ex. Word) and new wording will be indicated in Bold type (ex. Word).

Affected Sections:	Section 5.3 Exclusion Criteria, Item 7	
	Each subject must not meet any of the following exclusion criteria to be eligible for enrollment in the study:	
Original Text:	7. Subjects has the following laboratory parameters at screening by central laboratory:	
	a. creatinine, total bilirubin, international normalized ratio (INR) or prothrombin time above the upper limit of normal (ULN)	
	Each subject must not meet any of the following exclusion criteria to be eligible for enrollment in the study:	
Amended Text:	7. Subjects has the following laboratory parameters at screening by central laboratory:	
	a. creatinine or total bilirubin above the upper limit of normal (ULN), OR international normalized ratio (INR) above 1.1x ULN	
Rationale:	Based on the comparison of coagulation data in the same patient population from the central laboratory for this study and those from a different central laboratory and a certified local clinical laboratory, the central laboratory for this study reported higher PT results that were not considered either clinically significant or	
	exclusive. INR is a standardized calculation based on the PT result of the specific sample versus the PT result of a reference sample. INR has been recognized extensively as a standardized marker to evaluate coagulation function in patients	

	with all stages of liver diseases. Changes avoid unnecessary and medically inaccurate exclusion of eligible subjects for this study.
Categorization:	Non-substantial
Affected Sections:	Appendix 2 Part One/Two Schedule of Assessments (SoA) for Planned and Optional Cohorts in Subjects with Chronic HBV Infection, Footnote h of Vital signs
Original Text:	On Day 1, vital signs should be measured within 2 hours predose and 4 hours post-dose.
Amended Text:	On Day 1, vital signs should be measured within 2 hours predose and 4 hours (± 30 minutes) post-dose.
Rationale:	Clarification on the time window for collection of vital signs post-dose on Day 1.
Categorization:	Non-substantial
Affected Sections:	Appendix 2 Part One/Two Schedule of Assessments (SoA) for Planned and Optional Cohorts in Subjects with Chronic HBV Infection, Footnote j of Pregnancy test
Original Text:	A blood pregnancy test will be performed at screening and urine pregnancy tests will be performed thereafter.
Amended Text:	A blood pregnancy test will be performed at screening and urine pregnancy tests will be performed thereafter. Urine pregnancy test results from local laboratories are acceptable.
Rationale:	Clarification on allowing local laboratory results for urine pregnancy tests.
Categorization:	Non-substantial
Affected Sections:	Appendix 3 Part One/Two Pharmacokinetic Assessment Timepoints

Amended Text: Converted from the tabular format: PK blood will be collected at 1 hour (± minutes), 2 hours (± 10 minutes), 4 hours (± 30 minutes), 8 hours (± 30 minutes), and 24 hours (± 2 hours) post-dose on Day 1 and Week 4.	
Rationale:	Clarification on the time windows for PK sample collections.
Categorization:	Non-substantial
Affected Sections:	Section 8.3.2 Serious Adverse Events
	Email or fax the SAE form within 24 hours of the investigator's knowledge of the event. Contact information is as follows:
Original Text:	PPD
Amended Text:	Email or fax the SAE form within 24 hours of the investigator's knowledge of the event. Contact information is as follows:
Rationale:	Changes reflect the correct information of SAE reporting contact.
Categorization:	Non-substantial
Affected Sections:	Section 8.5.2 Special Situations Reports
Original Touts	All other special situations must be reported to PRA Pharmacovigilance within 24 hours of the investigator becoming aware of the situation. Contact information is as follows:
Original Text:	PPD
Amended Text:	All other special situations must be reported to PRA Pharmacovigilance the Sponsor within 24 hours of the investigator becoming aware of the situation. Contact information is as follows:
	PPD

Rationale:	Changes reflect the correct information of special situations reporting contact.
Categorization:	Non-substantial

## PROTOCOL SYNOPSIS

A Phase 2 Randomized, Placebo-Controlled Study in Mainland China to Evaluate the Safety, Tolerability, Pharmacokinetics and Antiviral Activity of VIR-2218	
Planned to be conducted at multiple clinical investigative sites in mainland China.	
Phase 2	
Up to 30 subjects	
Up to 30 adult subjects with HBeAg-negative or HBeAg-positive chronic hepatitis B virus (HBV) without cirrhosis on nucleos(t)ide reverse transcriptase inhibitor (NrtI) therapy.	
Adult subjects with chronic HBV infection without cirrhosis on NrtI therapy.	
Inclusive of screening to post-dose follow-up, the estimated total time on study for each subject is up to 20 weeks: screening period (4 weeks), dosing period (4 weeks) and post-dose follow-up period (12 weeks).	
Additional HBsAg monitoring is required for subjects with a $\geq 1$ $\log_{10}$ change from baseline (Day 1 predose level) decrease in HBsAg achieved by the Week 16 visit. Subjects will be followed until the HBsAg level returns to $> 90\%$ of the Day 1 predose level or Week 48, whichever comes earlier. Additional HBsAg monitoring may be discontinued at the Sponsor's discretion based on emerging data.	
Post-dose follow-up period:	
All subjects will be followed until Week 16.	
Extended follow-up period:	
Extended follow-up visits will occur every 4 weeks starting at Week 20 and up to Week 48.	

### Objective(s):

### Primary objective:

 To evaluate the safety and tolerability of multiple doses of VIR-2218 in subjects with HBeAg-negative and HBeAg-positive chronic HBV infection without cirrhosis on NrtI therapy

### Secondary objectives:

- To characterize the pharmacokinetics (PK) of VIR-2218 in subjects with chronic HBV infection without cirrhosis on NrtI therapy
- To assess the antiviral activity of VIR-2218 in subjects with chronic HBV infection without cirrhosis on NrtI therapy

### **Study Design:**

This is a phase 2 randomized, double-blind, placebo-controlled study of VIR-2218 administrated subcutaneously to adult subjects with chronic HBV infection without cirrhosis on NrtI therapy. The study is designed to evaluate the safety, tolerability, PK and antiviral activity of VIR-2218.

This study will be conducted in close collaboration with an ongoing phase 1/2 regional study (VIR-2218-1001, ClinicalTrials.gov Identifier: NCT03672188) conducted at multiple sites in the Asia-Pacific region. The objective of the VIR-2218-1001 regional study is to evaluate safety, tolerability, PK and antiviral activity of VIR-2218 in healthy volunteers (HVs) and patients with chronic HBV infection. The VIR-2218-1001 regional study includes 3 Parts, which are a single ascending dose (SAD) study in HV adult subjects (Part A), and two multiple ascending dose (MAD) studies in adult subjects with HBeAg-negative (Part B) and HBeAg-positive (Part C) chronic HBV infection without cirrhosis on NrtI therapy, respectively. Safety and efficacy data collected from the VIR-2218-1001 regional study will be used to guide the conduct of this study.

A Safety Review Committee (SRC) will perform ongoing reviews of safety and tolerability based on data collected through both this study and the VIR-2218-1001 regional study.

This study (VIR-2218-1005) will include two Parts:

- Part One: adult subjects with HBeAg-negative chronic HBV infection without cirrhosis on NrtI therapy for ≥ 6 months and HBV DNA < 90 IU/mL at screening (by central laboratory)
- Part Two: adult subjects with HBeAg-positive chronic HBV infection without cirrhosis on NrtI therapy for ≥ 6 months and HBV DNA < 90 IU/mL at screening (by central laboratory)

The cohort dosing strategy of this study is based on data collected from the VIR-2218-1001 regional study. There are two planned cohorts (50 mg dose-level and 100 mg dose-level) for each of Part One and Part Two of the study. For each of the planned cohorts, 5 subjects will be randomized 4:1 to VIR-2218 or placebo administered 4 weeks apart on Day 1 and Week 4.

One optional cohort may be added to each study Part One and Part Two, wherein 5 subjects will be randomized 4:1 to VIR-2218 or placebo, administered on Day 1 and Week 4 at a maximum doselevel of up to 200 mg.

The optional cohorts may be initiated after SRC review of a minimum of 6 weeks of available safety and antiviral activity data from the 200 mg cohorts of the VIR-2218-1001 regional study.

### **Study Procedures:**

### **Screening period:**

Screening will be performed no more than 4 weeks before the Day 1 visit and will include written informed consent, determination of eligibility, collection of demographics and medical history as well as physical examination (including vitals), laboratory tests, 12-lead Electrocardiogram (ECG) and other assessments per the schedule of assessments. Adverse events related to screening activities must be collected from the time of consent onwards; any other events occurring during the screening period should be reported as medical history. All serious adverse events (SAEs) must be collected from the time of consent onwards.

### **Dosing period:**

The dosing period is outpatient. Eligible subjects will be randomized to receive VIR-2218 or placebo within 48 hours before study drug administration on Day 1. Subjects will return to the clinical investigational site at Week 4 to receive a second dose of the same study drug administered on Day 1.

For subjects enrolled into the optional cohorts, eligible subjects will be randomized to receive VIR-2218 or placebo within 48 hours before study drug administration on Day 1. Subjects will return to the

clinical investigational site at Week 4 to receive a second dose of the same study drug administered on Day 1.

### Post-dose follow-up period:

Subjects will return to the clinical investigative site on an outpatient basis for safety, tolerability, PK, and antiviral activity monitoring at specified timepoints during this Post dose Follow up period (Week 5 to Week 16). Additional HBsAg monitoring is required for subjects with a  $\geq 1 \log_{10}$  change from baseline (Day 1 predose level) decrease in HBsAg achieved by the Week 16 visit.

### **Extended follow-up period:**

Subjects who require additional HBsAg monitoring will return to the clinical investigational site for in-person assessments. Extended follow-up visits will occur every 4 weeks starting at Week 20, and subjects will be followed until the HBsAg level returns to > 90% of the Day 1 predose level or Week 48, whichever comes earlier. Additional HBsAg monitoring may be discontinued at the Sponsor's discretion based on emerging data.

### Investigational Product, Dose, and Mode of Administration:

VIR-2218 is a synthetic, chemically modified small interfering RNA (siRNA) targeting HBV RNA with a covalently attached triantennary N-acetylgalactosamine (GalNAc) ligand that allows for specific uptake by hepatocytes. VIR-2218 will be supplied as a sterile solution for subcutaneous injection at a free acid concentration of 200 mg/mL. The starting dose level for the planned Cohorts in Parts One and Two will be 50 mg and 100 mg; the maximum dose level in the optional cohorts will not exceed 200 mg.

### **Reference Therapy:**

Subjects randomized to placebo will be administered sterile, preservative-free normal saline 0.9% solution for subcutaneous injection.

# Criteria for Evaluation:

### **Primary Endpoints**

- Incidence of treatment-emergent adverse events (TEAEs)
- Clinical assessments including but not limited to laboratory test results

### Secondary Endpoints

• PK parameters of VIR-2218 and possible metabolites (may include, but not limited to, maximum plasma concentration, time to reach maximum concentration, area under the concentration versus time curve [to last measurable timepoint and to infinity], percent of area extrapolated, apparent terminal elimination half-life, clearance, and volume of distribution)

- Maximum reduction of serum HBsAg from Day 1 until 12 weeks post last dose
- Number of subjects with serum HBsAg loss at any timepoint
- Number of subjects with sustained serum HBsAg loss for greater than or equal to 6 months post last dose
- Number of subjects with anti-HBs seroconversion at any timepoint
- For HBeAg-positive subjects (Part Two only): number of subjects with HBeAg loss and/or anti-HBe seroconversion at any timepoint

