### 5.2. Inclusion Criteria

Each subject must meet all the following inclusion criteria at screening to be eligible for enrollment in the study. All laboratory test requirements for inclusion will be performed by central laboratory:

- 1. Age 18 (or age of legal consent, whichever is older) to 65 years at the time of screening
- 2. 12-lead ECG within normal limits; or, with no clinically significant abnormalities at screening, as determined by the clinical investigator
- 3. Female subjects must have a negative pregnancy test or confirmation of post-menopausal status. Post-menopausal status is defined as 12 months with no menses without alternative medical cause. Women of child-bearing potential (WOCBP) must have a negative serum pregnancy test (using central laboratory) at screening and a negative urine pregnancy test on Day 1, cannot be breast feeding, and must be willing to use highly effective methods of contraception 14 days before study drug administration through 12 weeks after last study drug administration. Refer to Section 6.6 for more information on highly effective methods of contraception.
- 4. Male subjects with female partners of child-bearing potential must agree to meet 1 of the following contraception requirements from the time of study drug administration until the last follow-up visit: vasectomy with documentation of azoospermia, or male condom use plus partner use of 1 of the contraceptive options listed for contraception for WOCBP. Male subjects must also agree not to donate sperm for the 12 weeks following last study drug administration. Refer to Section 6.6 for more information on highly effective methods of contraception.
- 5. Agrees to not donate blood during the duration of the study
- 6. Willing to comply with the study requirements and able to provide written informed consent
- 7. Weight  $\geq$  40 kg to  $\leq$  125 kg
- 8. Chronic HBV infection as defined by a positive serum HBsAg for  $\geq 6$  months

- 9. On NrtI therapy for at least 6 months
- 10. HBsAg > 150 IU/mL
- 11. HBV DNA < 90 IU/mL
- 12. Part One only: HBeAg-negative
- 13. Part Two only: HBeAg-positive
- 14. Agrees not to increase physical activity from the time of screening through 4 weeks after final administration of VIR-2218

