Blood sample for HBsAg	X	X	X	X	X	X	X	X	X	X	X	X	X	X	X	X
Blood sample for anti-HBs	X										X		X		X	Xs
Blood sample for HBeAg qualitative	X															
Blood sample for HBeAg quantitative for Part Two only t		X					X				X	X	X		X	Xs
Blood sample for anti-HBe for Part Two only	X										X		X		X	Xs
Blood sample for HBV DNA quantitation u	X	X					X				X	X	X	X	X	Xs

Study Stage	Screening		Dosing Period					Post-dose Follow-up Period b				b	Extended Follow-up Period °			
Study Visit Week				W1	W2	W3	W4ª	W5	W6	W7	W8	W12	W16/ET	W20	W24	
Study Visit Day	D-28 to -1	D1ª	D2	D8	D15	D22	D29a	D36	D43	D50	D57	D85	D113	D141	D169	Q28D
±Visit Window				±2	±2	±2	±2	±2	±2	±2	±2	±7	±7/ET	±7	±7	±7

Review/record AEs x	X	
Concomitant Medications	X	
NrtI medication adherence	X	

AE = adverse event; ECG = electrocardiogram; ET = early termination; CCI surface antigen; HBV = Hepatitis B Virus; NrtI = nucleoside/nucleotide; PK = pharmacokinetics

HBeAg = hepatitis e-antigen; HBsAg = hepatitis B

Note: When scheduled at the same timepoints, the assessments of vital signs and 12-lead ECGs must be performed before blood sample collections.

- a Assessments performed predose unless otherwise specified.
- b If a subject withdraws prematurely from the study prior to their Week 16 visit, ET assessments should be performed.
- Additional HBsAg monitoring is required for subjects with  $a \ge 1 \log_{10}$  change from baseline (Day 1 predose level) decrease in HBsAg achieved by the Week 16 visit. Extended follow-up visits will occur every 4 weeks starting at Week 20, and subjects will be followed until the HBsAg level returns to > 90% of the Day 1 predose level or Week 48, whichever comes earlier. Additional HBsAg monitoring may be discontinued at the Sponsor's discretion based on emerging data.
- d A complete medical history will be taken at screening including HBV genotype if available. Any changes should be updated prior to dosing.
- e Evaluation of inclusion and exclusion criteria related to pregnancy testing, urine drug screen, medical history and concomitant medications prior to dosing.
- See Section 7.2.1 for assessments to be performed during a full physical examination.
- g Subjects' alcohol intake will be recorded while on study.

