- Vital signs (blood pressure, pulse rate, respiratory rate, and temperature) should be measured in the supine position after the subject has rested comfortably for approximately 10 minutes. On Day 1, vital signs should be measured within 2 hours predose and 4 hours (± 30 minutes) post-dose. On all other visit days, vital signs are only required to be recorded once during the visit.
- i 12-lead safety ECGs should be measured in the supine position after the subject has rested comfortably for 10 minutes.

cal Study Protocol Amendment 2

[figure not shown]
- WOCBP are required to have pregnancy tests. A blood pregnancy test will be performed at screening and urine pregnancy tests will be performed thereafter. Urine pregnancy test results from local laboratories are acceptable. Negative pregnancy test must be confirmed prior to study drug administration.
- boes not need to be performed if the subject has had a FibroScan in the 6 months prior to screening or liver biopsy in the year prior to screening that confirmed the absence of Metavir F3 fibrosis or F4 cirrhosis.
- See Section 7.1.3 for viral serology parameters.
- m Clinical laboratory and urinalysis parameters are described in Section 7.2.7.
- n Liver function tests only.
- Orugs of abuse included in the screen are described in the inclusion/exclusion criteria. Screening results for drugs of abuse must be reviewed prior to dosing.
- P Study drug will be administered via SC injection as described in Section 6.2.4.
- q Blood samples for PK analysis will be collected at the timepoints listed in Appendix 3.
- As a part of the Week 4 visit, subjects will return to the study center 24-hours after their initial post dose Week 4 PK sample is drawn to have a 24-hour post dose PK sample drawn.
- s Testing should occur again only at Week 36 and Week 48.
- For subjects in Part Two, if HBeAg has become undetectable for 2 consecutive assessments, no further quantitative testing is needed.
- u If a subject experiences ALT flare (as defined by ALT > 2x ULN) additional HBV DNA quantitation sample(s) may be collected
- v CCI
- w CCI
- All AEs related to screening activities must be collected from the time of consent onwards; any other events occurring during the screening period should be reported as medical history. All SAEs must be collected from the time of consent onwards.

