3.2 Key Definitions

The following definitions will be used:

- **Baseline:** The baseline value is defined as the last available valid (quantifiable continuous or categorical value), non-missing observation for each subject prior to first study drug administration. Repeat and unscheduled assessments will be included in the derivation of the baseline values.
- **Change from Baseline:** The change from baseline value is defined as the difference between the result collected/derived at a post-baseline visit/time point and the baseline value.

The change from baseline value at each post-baseline visit/time point will be calculated for all continuous parameters using the following formula:

$$\text{Change from Baseline Value} = \text{Result at Visit/Time Point} - \text{Baseline Value}$$

The change from baseline value will only be calculated if the specific post-baseline visit/time point result and the baseline value for the parameter are both available and will be treated as missing otherwise.

- **Study day:** The study day of an event is defined as the relative day of the event starting with the date of the first study drug administration (reference date) as Day 1 (there will be no Day 0).

The study day of events occurring before the first study drug administration will be calculated as:

$$\text{Study Day} = (\text{Date of Event} - \text{Date of First Study Drug Administration})$$

For events occurring on or after Day 1, study day will be calculated as:

$$\text{Study Day} = (\text{Date of Event} - \text{Date of First Study Drug Administration}) + 1$$

Study days will only be calculated for events with complete dates and will be undefined for events that are 'Ongoing' at the end of the study.

Relative days compared to an alternative reference point will be calculated similarly, but the alternative starting reference start date will be used instead of the date of the first study drug dosing.

- **HBsAg loss:** quantitative HBsAg < 0.05 IU/mL at two or more consecutive measurements.
- **Sustained HBsAg loss:** quantitative HBsAg < 0.05 IU/mL at all visits (scheduled and unscheduled) for ≥ 6 months.

- HBsAg Seroconversion: HBsAg loss plus anti-HBs positivity at two or more consecutive measurements
- HBeAg loss (HBeAg+ subjects only): quantitative HBeAg < 0.14 IU/mL at two or more consecutive measurements
- HBeAg Seroconversion (HBeAg+ subjects only): HBeAg loss plus anti-HBe positivity at two or more consecutive measurements

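### The SAP rule for HBeAg loss in Part Two needs no Day 1 value at or above 0.14 IU/mL and no post-dose limit, so a subject who was already low can be counted

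*Protocol*

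**What the plan says.** - **Endpoint.** Protocol Section 3.2 and the synopsis list "For HBeAg-positive subjects (Part Two only): number of subjects with HBeAg loss and/or anti-HBe seroconversion at any timepoint". SAP Section 13.1 repeats the count and adds no condition.
- **Entry.** Inclusion criterion 13 (Protocol Section 5.2) reads "Part Two only: HBeAg-positive". It sets no quantitative minimum.
- **Tests.** In the Schedule of Assessments (Protocol Appendix 2), the row "Blood sample for HBeAg qualitative" is marked at screening only, which spans Day -28 to Day -1. The row "Blood sample for HBeAg quantitative for Part Two only" starts on Day 1 and continues at Weeks 4, 8, 12 and 16. For subjects in extended follow-up it adds Weeks 24, 36 and 48. Footnote a makes the Day 1 sample predose: "Assessments performed predose unless otherwise specified".
- **Loss.** SAP Section 3.2: "HBeAg loss (HBeAg+ subjects only): quantitative HBeAg < 0.14 IU/mL at two or more consecutive measurements".
- **Seroconversion.** SAP Section 3.2: "HBeAg Seroconversion (HBeAg+ subjects only): HBeAg loss plus anti-HBe positivity at two or more consecutive measurements".
- **End of testing.** Appendix 2 footnote t, for Part Two: "if HBeAg has become undetectable for 2 consecutive assessments, no further quantitative testing is needed".

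**The concern.** The endpoint is meant to show HBeAg disappearing on study. The scoring rule looks only for two adjacent low values. It does not ask whether HBeAg was at or above the threshold before dosing, and it does not say that both values must be post-dose. Entry does not supply the missing condition, because the qualitative screening result carries no stated relation to 0.14 IU/mL and may be four weeks old. A subject whose HBeAg is already under the threshold on Day 1 and stays there has nothing to lose on this scale, yet meets the definition.

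Seroconversion is built on loss, so it takes over the same gap. Neither Section 5.2 nor Section 5.3 of the Protocol excludes subjects who are anti-HBe positive at screening. With cohorts of five, a single such subject visibly changes the reported percentage.

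**Working it through.** **1. Group sizes.** Protocol Section 4.1 gives 5 subjects per cohort, randomised 4:1, with two planned cohorts and one optional cohort per part. Part Two is therefore at most 3 × 5 = 15, which reproduces the figure in Protocol Section 5.1. Active subjects number 2 × 4 = 8, or 3 × 4 = 12 with the optional cohort. Placebo subjects number 2 or 3.

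**2. The rule applied to example profiles.** The profiles are illustrative, on the schedule Day 1, Weeks 4, 8, 12 and 16.

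| HBeAg profile (threshold 0.14 IU/mL) | SAP text | Post-dose pairs only | Day 1 ≥ 0.14 and post-dose pairs |
|---|---|---|---|
| Below at every visit, no change | loss | loss | not counted |
| Below on Day 1 and Week 4, above afterwards | loss | not counted | not counted |
| Below on Day 1 only | not loss | not loss | not counted |
| Above on Day 1, below at Weeks 8 to 16 | loss | loss | loss |

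The first two rows are the problem. The third shows that a low Day 1 value does not score by itself. The third column shows that a post-dose limit alone is not enough, because the subject who is low throughout is still counted. The Day 1 condition does most of the work, and the genuine loss in the last row is unaffected by it.

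**3. Other text that might supply the condition.**
- SAP Section 3.6 uses HBeAg+ as the label for Part Two, so that restriction in the loss definition can be read as Part Two membership, which follows the screening result.
- SAP Section 3.2 defines baseline as a valid quantifiable or categorical value, but the loss definition does not refer to baseline.
- SAP Section 4.1.4 admits a subject to the Antiviral Analysis Set with one non-missing, interpretable result.
- Appendix 2 footnote e limits the Day 1 eligibility check to pregnancy testing, drug screen, medical history and concomitant medication. A low Day 1 HBeAg therefore changes nothing.
- HBsAg is different. Entry requires more than 150 IU/mL and loss is set at under 0.05 IU/mL, so HBsAg loss is guarded against the same error.

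**4. Weight of one subject (100/n).** Active cohort of 4: 25.0 points. All active: 12.5 points (n = 8) or 8.3 points (n = 12). Placebo: 50.0 points (n = 2) or 33.3 points (n = 3). All of Part Two at 15: 6.7 points.

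**5. How likely.** Let q be the share of Part Two subjects below 0.14 IU/mL on Day 1. The documents give no value, so the values below are assumptions. The chance that at least one of n subjects is low on Day 1 is 1 − (1 − q)^n.

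| q (assumed) | n = 4 | n = 8 | n = 12 |
|---|---|---|---|
| 2% | 7.8% | 14.9% | 21.5% |
| 5% | 18.5% | 33.7% | 46.0% |
| 10% | 34.4% | 57.0% | 71.8% |
| 20% | 59.0% | 83.2% | 93.1% |

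For each assumed q these are upper bounds on the chance of a loss scored this way, because a low Day 1 value must be joined by a low Week 4 value or by two later low values in a row.

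**The case against.** **Confirmation already protects.** Two consecutive values are needed, which filters out isolated noise near the threshold. This stands. A reader might infer that any subject low on Day 1 is counted, and the text does not say so. Confirmation does not help with a subject who is steadily low.

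**No evidence that such subjects exist.** A reader might infer that the screening and Day 1 results come from different assays that will disagree. The documents do not say so. They give no qualitative cut-off, and Protocol Section 7.1.2 leaves analysis details to the Laboratory Manual. If platform and cut-off are shared, disagreement is limited to change or variation over at most 28 days. This stands: q is unknown and may be small.

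**The intent is clear.** The word *loss*, the HBeAg+ restriction, HBeAg Baseline Status among the SAP Section 7.1.1 variables, and the wording of footnote t all suggest a change from a positive start. The requirement of interpretable data in SAP Section 4.1.4 might also be used to set such a subject aside. These are fair readings of intent, but none is a stated condition. Baseline status can be met by the categorical screening result, and footnote t governs sampling, speaks of undetectable HBeAg rather than 0.14 IU/mL, and does not score the endpoint.

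**The case would be visible.** The study is descriptive (SAP Section 3.3), all antiviral data are listed, and SAP Section 13.2 plans individual HBeAg plots for Part Two and categorical results at baseline. This stands and lowers the severity, but the tabulated count would still include the subject.

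**Bias toward VIR-2218.** With 4:1 allocation a reader might infer that the gap favours the active arm. It does not follow. Randomisation gives the same expected proportion in both arms, and one placebo case weighs more (33% to 50%) than one case in an active cohort (25%).

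**Conclusion.** The gap is real and minor. Under the SAP text, a Part Two subject below 0.14 IU/mL on Day 1 who is also below at Week 4, or at two later consecutive visits, is counted as HBeAg loss and can feed HBeAg seroconversion, with no fall from the Day 1 level required. Footnote t may also let quantitative testing end after Week 4 if both values are undetectable, so a later rise might not be measured.

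One such subject moves an active cohort by 25 points and the Part Two placebo group by 33 or 50 points, so the distortion can go either way. The frequency rests wholly on an assumed q. The tabulated chances should not be read as the probability of a false loss, and they say nothing about whether q is above zero. No alpha or power is affected.

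**What to change.** In SAP Sections 3.2 and 13.1, count HBeAg loss and HBeAg seroconversion only in Part Two subjects whose Day 1 predose quantitative HBeAg is at least 0.14 IU/mL, and require both confirming HBeAg measurements to follow the first dose. List subjects below 0.14 IU/mL on Day 1 separately. Either leave them out of the denominator or show them as non-events with a footnote; both are acceptable if the choice is fixed before database lock and unblinding, when SAP Section 16.2 already requires the SAP and analysis sets to be approved.

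The cost is a short wording change and one programming condition on data already scheduled for collection. Eligibility and sampling stay as they are. The downside is a slightly smaller denominator if the excluding option is chosen: for example, 3 instead of 4 in an active cohort with one such subject.
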